This prospective, open-label, single-arm, single-center clinical study at the University of California, San Diego Department of Dermatology is designed primarily to investigate the safety and efficacy of deoxycholic acid injection for the treatment of upper inner thigh fat. The secondary objective of this study is evaluation of patient-reported satisfaction outcomes after treatment of upper inner thigh fat with deoxycholic acid injection.

III. Subject Selection

A. Inclusion/Exclusion criteria

Inclusion

- 1. Adults aged 18 to 65
- 2. Discrete area of mild-to-moderate excess upper inner thigh fat, amenable to treatment at the discretion of the investigator
- 3. Subjects who score 0 (extremely dissatisfied) to 2 (slightly dissatisfied) on a Subject Self-Rating Scale, pertaining to upper inner thigh fat, with the scale ranging from 0 (extremely dissatisfied) to 6 (extremely satisfied)
- 4. Body mass index (BMI) less than 30 kg/m²
- 5. Stable body weight for previous 6 months (weight within 10 pounds of baseline)
- 6. Subjects must be in stable health, as confirmed by medical history, per investigator judgment
- 7. Subjects must be able to read, sign, and understand the informed consent
- 8. Subjects must we willing to avoid any other treatments to the inner thigh, including cryolipolysis and liposuction, during the study period.
- 9. Subjects must be willing to avoid changes in diet or exercise, any weight loss program, and any weight loss supplements, during the study period.
- 10. Subjects must be able and willing to avoid anticoagulation (aspirin, warfarin, hepain, rivaroxaban) for 1 week prior to each study treatment

Exclusion:

1. History of treatment for inner thigh fat, including cryolipolysis, noninvasive body contouring or liposuction in the last year

- 2. Previous trauma or surgery to pelvis or thighs
- 3. Subjects with an unstable medical condition, as deemed by the investigator
- 4. Women who are pregnant or lactating or plan to become pregnant during the study period
- 5. Lymphedema or edema of thigh
- 6. Excessive skin laxity in the treatment area, as judged by the investigator
- 7. Severe thigh cellulite
- 8. Subjects with any disease in the treatment area, such as dermatologic disease, that may be exacerbated by the study treatment
- 9. Subjects with any condition that may impair the evaluation of inner thigh fat
- 10. Subjects with known bleeding diathesis

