- 11. Subjects with any known hypersensitivity to Kybella (deoxycholic acid) or any of the inactive ingredients: benzyl alcohol, dibasic sodium phosphate, sodium chloride, sodium hydroxide, hydrochloric acid
 - B. Source of subjects and recruitment methods
 Subjects will be recruited by flyers and handouts placed in the UCSD Dermatology
 clinic. Eligible patients will be determined from the inclusion and exclusion criteria.
 Eligible patients will be informed of the proposed study and its purpose and given the
 opportunity to ask any questions.

Standard HIPAA authorization to collect research data from the subject's medical record will be obtained at the time of informed consent.

C. Equitable Selection of Subjects

The risks and benefits of the research are fairly distributed among the populations that stand to benefit from it. Although the risk of this study is minimal, to be prudent, pregnant women will be excluded because of the potential harm posed to the fetus.

IV. Subject Enrollment

A. Number of subjects

15 subjects will be enrolled in the study.

B. Methods of enrollment

Subjects interested in participating in the study may contact one of the investigators. The study objectives, inclusion and exclusion criteria, possible risks and benefits of the study, and the information included in the informed consent form shall be discussed with prospective study participants. Subjects who believe they meet the exclusion and inclusion criteria and remain interested in the study shall be invited to come in for their screening visit. During the screening visit, the investigator will interview the subject and perform a simple clinical examination, particularly examining the thighs. Following the investigator's determination that the inclusion and exclusion criteria are met, the subject be invited to participate in the study.

C. Procedures for obtaining informed consent

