There will be no randomization. Study participants will be treated with deoxycholic acid (Kybella) 10 mg/ mL injected subcutaneously, targeting the medial thigh deep fat compartment (pre-fascial). Subjects will receive deoxycholic acid 2 mg/ cm², with injections of 0.2 mL spaced evenly 1 cm apart within the treatment area. Bilateral upper inner thighs will be treated. Each treatment will consist of a maximum of 8 mL (40 injection sites) of the study drug, with a maximum of 4 mL (20 injection sites) of the study drug for each thigh. All treatments will be performed by a study physician. Subjects will receive 1 to 4 treatment sessions, each spaced 6 weeks +/- 1 week. Treatment #2, #3, or #4 will be pursued if patient desires more treatment, and if there is sufficient fat for treatment, per investigator's judgment.

V. Study Procedures

a) Study visits and parameters to be measured
 All visits in this study will be performed at the UCSD Dermatology Clinic, 3rd floor,
 [name].

Screening/Baseline Visit (Visit 1, Day -14 to 1)

This visit is expected to take approximately 1 hour. The following describes the procedures performed at this visit.

Prior to any screening assessments, informed consent will be obtained by the
investigator. When the subject fully understands the nature of the study and its risks,
the subject will be asked to sign and date the informed consent form. The
investigator will then sign and date the form.

- 2. A detailed medical history of information pertaining to treatment will be obtained.
- 3. The investigator will perform a relevant physical examination.
- 4. Patient's weight will be obtained.
- 5. The subject will be asked to complete the Subject Self-Rating Scale (0 to 6 scale).
- 6. If the subject meets the criteria for the study, the subject will be assigned the next consecutive subject number.
- 7. Females of childbearing age will undergo a urine pregnancy test
- 8. The investigator will determine the patient's eligibility for the study.

First treatment (Visit 2, Day 1)

The treatment visit is expected to take approximately 1 hour. The first treatment may be combined with Screening/ Baseline.

Prior to Kybella treatment:

- 1. Patient will be asked to complete the Subject Self-Rating Scale, rated from 0 to 6.
- 2. Patient's weight will be obtained.
- 3. Concomitant medications and procedures will be confirmed and recorded.
- 4. The investigator will perform a relevant physical examination.

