 Vertical distance of this site from the floor will be measured, such that thigh circumference measurements at all following study assessments are performed at the same site.

- 7. Caliper measurement of inner thigh skin-fold thickness will be obtained.
- Caliper measurement will be performed at site of maximum bulge at Screening.
 Vertical distance of this site from the floor will be measured, such that caliper measurements at all following study assessments are performed at the same site.
- 8. Thigh gap measurement will be obtained.
- Patient will be asked to stand with legs at a fixed distance apart. Measurement
 will be performed between sites of maximum bulge at Screening. Vertical
 distance of these sites from the floor will be measured, such that thigh gap
 measurements at all following study assessments are performed at the same sites.
- 9. Pre-treatment photographs will be taken.
- Patients will be asked to stand with feet apart at a uniform distance.
 Anteroposterior and posteroanterior photos will be taken.

Treatment:

10. Deoxycholic acid (Kybella) 10 mg/ mL will be injected subcutaneously, targeting the medial thigh deep fat compartment (pre-fascial). Subjects will receive deoxycholic acid 2 mg/ cm2, with injections of 0.2 mL spaced evenly 1 cm apart within the treatment area. Bilateral thighs will be treated. Each treatment will consist of a maximum of 8 mL (40 injection sites) of the study drug, with a maximum of 4 mL (20 injection sites) of the study drug for each thigh. All treatments will be performed by a study physician.

Post-Treatment Phone Call #4 (~Day 108 to 150)

Phone call expected to take 5-10 minutes.

1. Two days after treatment, patient will be called and asked to report adverse events since last treatment. All adverse events will be recorded.

Week 4 Follow Up (~Day 134 to 176)

Visit expected to take 1 hour. The visit will take place 4 weeks after the last treatment.

- 1. Patient will be asked to complete Subject Self-Rating Scale, rated from 0 to 6.
- 2. Patient will be asked to complete Post-Treatment Satisfaction Questionnaire.
- 3. Concomitant meds and procedures will be confirmed and recorded.
- 4. Adverse events will be confirmed and recorded.
- 5. Patient weight will be obtained.
- 6. A relevant physical exam will be performed by the investigator.
- 7. Thigh circumference measurement will be obtained with anthropometric tape measure.
 - Thigh circumference will be measured at site of maximum bulge at Screening.

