Common side effects of deoxycholic acid injection are injection site reactions, including swelling, pain, numbness, redness, and hardness of treatment area. Bruising, itching, warmth, hardness, tingling or burning sensation, skin tightness, hair loss, open sores (ulcers), damage, and tissue cell-death (necrosis) around the injection site are other possible side effects.

Deoxycholic acid injection in submental fat has been rarely associated with nerve injury, headache, mouth or throat pain, hypertension, nausea, or difficulty swallowing.

Patients will be asked regarding allergy to medications. Allergic reaction may occur with any medication.

Subjects will be provided post-treatment instructions (see attached).

B. Psychosocial (non-medical) risks

We do not anticipate any psychosocial risks due to this study. However, if any participants experience emotional distress during the study we will assist them to resolve this stress with appropriate referrals. Steps to prevent this outcome will include detailed explanation of the study and what to expect from the study treatment.

VIII. Potential Benefits

A. Potential benefits to participating individuals

Subjects participating in the study may receive the benefit of reduced inner thigh fat due to the study treatment.

B. Potential benefits to society

The results of this study will help us acquire information that may lead to the development of a new treatment for reduction of inner thigh fat.

IX. Cost and Remuneration

a. Remuneration

Subjects will receive financial compensation for their participation in the study.

Screening and treatment visits will not be compensated. Subjects will receive \$50 per inperson follow-up visit. Therefore, subjects will receive a total of \$100 for completing the entire study.

b. Cost

There will be no cost to the patient to participate in this study.

X. Monitoring and Quality Assurance

A. Independent monitoring of source data

At this time, we do not anticipate a need for an independent monitor as our monitoring of the data will be sufficient to ensure the validity and integrity of the data and adherence to the IRB-approved protocol.

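### Entry criteria are discussed before subjects complete the self-rating that both admits them and serves as baseline, so the self-rated improvement (endpoint b.i) could be biased upward.

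*Combined protocol and SAP*

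**What the plan says.** The relevant provisions of the combined protocol and SAP, in the order a subject meets them:

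- **IV.B Methods of enrollment** (repeated in substance in X.A): the "inclusion and exclusion criteria, possible risks and benefits of the study, and the information included in the informed consent form shall be discussed with prospective" participants. It continues: "Subjects who believe they meet the exclusion and inclusion criteria and remain interested in the study shall be invited to come in" for the screening visit. No criterion is exempted from this discussion.
- **III.A, inclusion criterion 3**: "Subjects who score 0 (extremely dissatisfied) to 2 (slightly dissatisfied) on a Subject Self-Rating Scale, pertaining to upper inner thigh fat". Appendix I labels every point of the scale; 2 is slight dissatisfaction and 3 is neutral.
- **V.a, Screening/Baseline Visit**: consent comes before any assessment. The self-rating is item 5, after history, physical examination and weight. IV.B says the screening examination looks particularly at the thighs.
- **V.a, all later visits**: the scale is item 1 at Visit 2, at Treatments 2 to 4, and at the Week 4 and Week 12 follow-ups ("Patient will be asked to complete Subject Self-Rating Scale, rated from 0 to 6").
- **VI.A, secondary endpoint b.i**: improvement on this scale. **VI.B** takes baseline values from the day of screening, which may coincide with Day 1, and reports the scores descriptively.
- **IX.b**: "There will be no cost to the patient to participate in this study".

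**The concern.** A subject may arrive at screening knowing which answers on a short, fully labelled scale lead to treatment. Moving from the neutral point to slight dissatisfaction is one step, and that step separates exclusion from one to four free treatment sessions. After entry, a low score gains the subject nothing: further sessions depend on the subject's wish and the investigator's judgement of remaining fat (IV.D), not on the score. An understated entry score followed by an honest later one appears as improvement without any drug effect.

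The bias can run in only one direction, and no control group shares it. Patient-reported satisfaction is the study's stated secondary objective (II.A), and b.i is the measure of it that depends on a baseline score. The Day 1 rating offers no protection. The subject still knows the criteria, the two visits may be combined, and VI.B names screening as the baseline.

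The difference in item order is a separate and smaller matter. The baseline is taken after the thighs have been discussed and examined, and every value compared with it is taken before.

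**Working it through.** The plan gives no expected change, standard deviation, power or sample-size derivation for this scale, so there is no stated figure to reproduce.

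**Step 1. Sequence.** Criteria discussed (IV.B, X.A), then invitation to screening, then consent, then history, examination and weight, then self-rating (V.a). III.B can be read as eligibility being determined first and patients informed afterwards. That does not change the order: IV.C bars study procedures before consent, and V.a puts the scale after consent.

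**Step 2. Effect of understating on the mean.** From the documents, n = 15 (IV.A). Assumed: m subjects understate their screening score by k points and later answer honestly, and each has a later rating. A subject whose screening value is carried forward under LOCF shows no change and adds nothing. Compared with the same 15 subjects answering honestly throughout, the mean improvement rises by m × k / 15.

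| m | k = 1 | k = 2 |
|---|---|---|
| 1 | 1/15 = 0.07 | 2/15 = 0.13 |
| 3 | 3/15 = 0.20 | 6/15 = 0.40 |
| 5 | 5/15 = 0.33 | 10/15 = 0.67 |
| 15 | 15/15 = 1.00 | 30/15 = 2.00 |

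The documents give no value for m or k.

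**Step 3. What would remain if the cut-off were withheld.** Selecting on the score that is also the baseline produces regression to the mean even when everyone is honest. A simulation with no treatment effect shows the split. All its inputs are assumed: ratings rounded and limited to 0–6, SD 1.3, population mean 1.5, 2.5 or 3.0, test-retest reliability 0.6, 0.8 or 0.9, and entry at a reported score of 2 or less. The table gives the spurious mean improvement.

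| Mean | Reliability | No understating | All honest 3s report 2 | Difference |
|---|---|---|---|---|
| 1.5 | 0.6 | 0.22 | 0.24 | 0.02 |
| 1.5 | 0.8 | 0.12 | 0.21 | 0.09 |
| 1.5 | 0.9 | 0.07 | 0.19 | 0.12 |
| 2.5 | 0.6 | 0.47 | 0.58 | 0.11 |
| 2.5 | 0.8 | 0.26 | 0.48 | 0.22 |
| 2.5 | 0.9 | 0.16 | 0.43 | 0.27 |
| 3.0 | 0.6 | 0.61 | 0.79 | 0.18 |
| 3.0 | 0.8 | 0.34 | 0.64 | 0.30 |
| 3.0 | 0.9 | 0.21 | 0.57 | 0.36 |

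In the middle case (mean 2.5, reliability 0.8), if 25% or 50% of honest 3s report 2, the result is 0.33 or 0.39, which is 0.07 or 0.13 above the 0.26 seen with no understating.

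Steps 2 and 3 answer different questions. Step 2 holds the 15 subjects fixed. Step 3 compares the groups that would be enrolled with and without understating.

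**Step 4. Which results use the score.** Only b.i does. The primary safety endpoint, tape, caliper, thigh gap, blinded photograph review and the Appendix II questionnaire do not.

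**The case against.** The strongest case on the other side has five parts.

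- **Disclosure is inferred.** No sentence says the numeric range is announced, and the consent form and recruitment materials are not available for review. This stands as a limit on certainty. It does not remove the point, because people cannot judge whether they meet criteria they have not been told, and nothing holds this one back.
- **Few subjects may be able to understate.** Volunteers must have excess fat in the investigator's judgement, accept up to 40 injection sites per session, and attend unpaid screening and treatment visits. Most may be honestly dissatisfied. This is plausible, and it is why no share can be asserted.
- **Other measures would expose a spurious gain.** A reader might infer that nothing else in the study could separate an understated entry score from real improvement. That goes too far: the physical measures, the blinded photographs and Appendix II do not use the entry score, so a self-rating gain with no change elsewhere would be visible. They do not correct b.i itself.
- **The remedy is partial.** A person seeking treatment can guess that dissatisfaction qualifies, and regression to the mean remains. Both parts stand. In the middle simulated case, the 0.26 points left without understating exceed the 0.22 that understating adds even when every honest 3 reports 2.
- **Item order is only a preference.** The documents give no direction or size for an order effect, so none is claimed. The inconsistency is nevertheless explicit and easily removed.

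**Conclusion.** The plan allows entry scores to be understated by subjects who know the criteria, and any understating would bias b.i upward. The addition to the mean is m/15 points when m subjects understate by one point. Its actual size is unknown and rests entirely on assumed behaviour. The issue is confined to one descriptive secondary endpoint with no test and no success threshold, although that endpoint serves the stated secondary objective.

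Two stronger readings are not supported. A reader might infer that the improvement is in fact inflated; the documents show only that it could be. A reader might also infer that subjects would be enrolled in breach of criterion 3. The criterion is the reported score itself, so a subject who reports 2 meets it as written.

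**What to change.** 1. In IV.B and X.A, and in the recruitment and consent wording if they state it, do not disclose which self-rating answers qualify until the scale has been completed. It is enough to say that a questionnaire about the thighs is completed at screening.
2. In the Screening/Baseline Visit list (V.a), move the Subject Self-Rating Scale to directly after consent, before history, examination and weighing. This matches its first position at every other visit.
3. When b.i is reported, state that subjects were selected on the score used as baseline, and that regression to the mean may account for part of any improvement. Items 1 and 2 do not remove this.

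The cost is a wording change in two sections and one reordered list. Any change to the consent form or written information needs IRB approval under IV.C. A few more people may attend an unpaid screening visit of about an hour and then fail criterion 3.

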- 5. Thigh circumference measurement will be obtained with anthropometric tape measure.
 - Thigh circumference will be measured at site of maximum bulge at Screening.
 Vertical distance of this site from the floor will be measured, such that thigh circumference measurements at all following study assessments are performed at the same site.
- 6. Caliper measurement of inner thigh skin-fold thickness will be obtained.

Caliper measurement will be performed at site of maximum bulge at Screening.
 Vertical distance of this site from the floor will be measured, such that caliper measurements at all following study assessments are performed at the same site.

- 7. Thigh gap measurement will be obtained.
 - Patient will be asked to stand with legs at a fixed distance apart. Measurement
 will be performed between sites of maximum bulge at Screening. Vertical
 distance of these sites from the floor will be measured, such that thigh gap
 measurements at all following study assessments are performed at the same sites.
- 8. Pre-treatment photographs will be taken.
 - Patients will be asked to stand with feet apart at a uniform distance.

 Anteroposterior and posteroanterior photos will be taken.

Treatment:

9. Deoxycholic acid (Kybella) 10 mg/ mL will be injected subcutaneously, targeting the medial thigh deep fat compartment (pre-fascial). Subjects will receive deoxycholic acid 2 mg/ cm2, with injections of 0.2 mL spaced evenly 1 cm apart within the treatment area. Bilateral thighs will be treated. Each treatment will consist of a maximum of 8 mL (40 injection sites) of the study drug, with a maximum of 4 mL (20 injection sites) of the study drug for each thigh. All treatments will be performed by a study physician.

Post-Treatment Phone Call #1 (Day 3)

Phone call expected to take 5-10 minutes.

1. Two days after treatment, patient will be called and asked to report adverse events since last treatment. All adverse events will be recorded.

Second treatment (+/-) (Day 36 to 50)

The treatment visit is expected to take approximately 1 hour.

Prior to Kybella treatment:

1. Patient will be asked to complete the Subject Self-Rating Scale, rated from 0 to 6.

- 2. Patient's weight will be obtained.
- 3. Concomitant medications and procedures will be confirmed and recorded.
- 4. Adverse events will be recorded.
- 5. The investigator will perform a relevant physical examination.
- 6. Thigh circumference measurement will be obtained with anthropometric tape measure.

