 - Thigh circumference will be measured at site of maximum bulge at Screening.
 Vertical distance of this site from the floor will be measured, such that thigh circumference measurements at all following study assessments are performed at the same site.
- 7. Caliper measurement of inner thigh skin-fold thickness will be obtained.
 - Caliper measurement will be performed at site of maximum bulge at Screening.
 Vertical distance of this site from the floor will be measured, such that caliper measurements at all following study assessments are performed at the same site.
- 8. Thigh gap measurement will be obtained.
 - Patient will be asked to stand with legs at a fixed distance apart. Measurement
 will be performed between sites of maximum bulge at Screening. Vertical
 distance of these sites from the floor will be measured, such that thigh gap
 measurements at all following study assessments are performed at the same sites.
- 9. Pre-treatment photographs will be taken.
 - Patients will be asked to stand with feet apart at a uniform distance.

 Anteroposterior and posteroanterior photos will be taken.

Treatment:

10. Deoxycholic acid (Kybella) 10 mg/ mL will be injected subcutaneously, targeting the medial thigh deep fat compartment (pre-fascial). Subjects will receive deoxycholic acid 2 mg/ cm2, with injections of 0.2 mL spaced evenly 1 cm apart within the treatment area. Bilateral thighs will be treated. Each treatment will consist of a maximum of 8 mL (40 injection sites) of the study drug, with a maximum of 4

mL (20 injection sites) of the study drug for each thigh. All treatments will be performed by a study physician.

Post-Treatment Phone Call #2 (Day 38 to 52)

Phone call expected to take 5-10 minutes.

1. Two days after treatment, patient will be called and asked to report adverse events since last treatment. All adverse events will be recorded.

Third Treatment (+/-) (Day 71 to 99)

The treatment visit is expected to take approximately 1 hour.

Prior to Kybella treatment:

- 1. Patient will be asked to complete the Subject Self-Rating Scale, rated from 0 to 6.
- 2. Patient's weight will be obtained.
- 3. Concomitant medications and procedures will be confirmed and recorded.
- 4. Adverse events will be recorded.
- 5. The investigator will perform a relevant physical examination.
- 6. Thigh circumference measurement will be obtained with anthropometric tape measure.
 - Thigh circumference will be measured at site of maximum bulge at Screening.

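### The itemised visit lists contain one pregnancy test, at Screening/Baseline, and no listed step before optional treatments 2, 3 and 4 looks for a pregnancy that began later (subject to the Schedule of Events and consent form, which were not available)

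*Combined protocol and SAP*

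**What the plan says.** Exclusion criterion 4 in section III.A of the combined protocol and SAP bars "Women who are pregnant or lactating or plan to become pregnant during the study period". Section III.C gives the reason: "Although the risk of this study is minimal, to be prudent, pregnant women will be excluded because of the potential harm posed to the fetus".

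The check that supports this criterion is item 7 of the first visit in section V.a: "Females of childbearing age will undergo a urine pregnancy test". That visit is headed "Screening/Baseline Visit (Visit 1, Day -14 to 1", and it may be combined with the first treatment on Day 1.

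Dosing then continues. Section IV.D states that "Subjects will receive 1 to 4 treatment sessions, each spaced 6 weeks +/- 1 week", and that treatments 2, 3 and 4 "will be pursued if patient desires more treatment, and if there is sufficient fat for treatment", the latter as judged by the investigator. Pregnancy status is not among these conditions.

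The pre-treatment lists for treatments 2, 3 and 4 in section V.a have the same content: the self-rating scale, weight, concomitant medications and procedures, adverse events, a physical examination, thigh circumference, caliper thickness, thigh gap and photographs. None names a pregnancy test or question.

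Section V.c refers to a Schedule of Events for the data to be collected. That schedule, the consent form and the post-treatment instructions are not in the text available for review.

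**The concern.** A screening test can find only a pregnancy that exists at screening. Excluding women who plan a pregnancy does not cover an unplanned one. Up to three further injection sessions follow, over several months, and no listed step before any of them looks for a pregnancy the subject does not yet know about.

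If staff follow the visit lists as written, a subject who conceived after screening could be injected again. This is the exposure that section III.C sets out to avoid. What is at stake is the safety of the participant and the fetus, not the validity of an estimate.

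**Working it through.** **Inputs.** All come from the combined protocol and SAP.
- Test date: Day -14 to Day 1 (section V.a, Screening/Baseline).
- First treatment: Day 1 (section V.a).
- Spacing: 6 weeks plus or minus 1 week, so 35 to 49 days, nominally 42 (section IV.D).
- Sessions: 1 to 4 per subject (section IV.D).
- Subjects: 15 (section IV.A).

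**Step 1: reproduce the plan's windows.** Treatment k falls between Day 1 + 35(k - 1) and Day 1 + 49(k - 1).
- Treatment 2: 1 + 35 = 36 to 1 + 49 = 50. The plan has "Second treatment (+/-) (Day 36 to 50".
- Treatment 3: 1 + 70 = 71 to 1 + 98 = 99. The plan has "Third Treatment (+/-) (Day 71 to 99".
- Treatment 4: 1 + 105 = 106 to 1 + 147 = 148. The plan has Day 106 to 148.

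All three agree.

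**Step 2: interval from the only listed test to each injection.** The plan does not define a Day 0. Assuming there is none, Day -14 is 14 days before Day 1.
- Nominal: 42(k - 1) if the test is on Day 1; 42(k - 1) + 14 if it is on Day -14.
- Shortest: 35(k - 1), with the test on Day 1 and every session as early as allowed.
- Longest: 49(k - 1) + 14, with the test on Day -14 and every session as late as allowed.

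| Treatment | Nominal (days) | Shortest (days) | Longest (days) |
|---|---|---|---|
| 2 | 42 to 42 + 14 = 56 | 36 - 1 = 35 | 49 + 14 = 63 |
| 3 | 84 to 84 + 14 = 98 | 71 - 1 = 70 | 98 + 14 = 112 |
| 4 | 126 to 126 + 14 = 140 | 106 - 1 = 105 | 147 + 14 = 161 |

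The full range is 35 to 161 days. If a Day 0 is counted, every figure that starts from Day -14 rises by one, so the longest intervals become 64, 113 and 162 days. The shortest do not change. For treatment 1 the interval is 0 to 14 days (15 with a Day 0).

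**Step 3: sessions affected, and kits.** At most 15 × 4 = 60 sessions are given, of which 15 × 3 = 45 (45/60 = 75%) are treatments 2 to 4. This is a ceiling. It assumes that every subject is a female of childbearing age and has all four sessions. It serves to cost the fix and does not measure risk. The documents give neither the number of such women nor a fetal-risk figure, so no risk is estimated.

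**Step 4: does a pregnancy stop affect the analysis?** Three provisions, read together:
- Component (c) of the primary endpoint (section VI.A) counts adverse events that lead to stopping the study drug. Nothing in the documents classes a pregnancy as an adverse event.
- Last observation carried forward (section VI.B) applies when a subject leaves the study early. Stopping injections is not leaving the study.
- Section IV.D allows as few as one session, and section V.a times the Week 4 and Week 12 visits from the last treatment.

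A subject who stops for pregnancy therefore has fewer sessions and the same follow-up.

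**The case against.** The strongest objection is that the decisive pages are unseen. Repeat tests, contraception advice or a duty to report pregnancy could well stand in the Schedule of Events, the consent form or the post-treatment instructions, and text that was not supplied cannot be called missing from the plan. This stands to the extent that the point must be conditional. It does not remove the point. The visit lists are detailed, they name the screening test, and they name no repeat. If the schedule does require repeats, the lists still need to match it.

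A second objection is that other safeguards exist. Each later treatment visit is in person, with weight, medications, adverse events and an examination recorded. Section X.B makes the principal investigator responsible for subjects' safety. A pregnancy that the subject knows of would probably come to light. But none of these steps is described as looking for an unrecognised one.

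A third is that no risk has been quantified, and that 161 days needs the earliest screening and the latest session dates. Both are fair, so the nominal intervals should lead, with the extremes as bounds.

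A reader might also infer that a pregnancy stop would inflate the primary endpoint by one subject in 15 (1/15 = 6.7 percentage points) or force imputation. The documents do not support this, for the reasons in the last step of the working.

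**Conclusion.** The point holds as a conditional gap in participant safety. The itemised visit lists provide for one pregnancy test, and the optional later injections come nominally 42 to 56, 84 to 98 and 126 to 140 days after it. The full range is 35 to 161 days, assuming no Day 0. No listed step in between looks for a pregnancy that began after screening. The conclusion depends on the Schedule of Events and consent form not already requiring repeat tests, which could not be checked.

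Two stronger readings should be resisted. One is that the protocol contradicts its own exclusion criterion. It does not: the criterion is tested at entry, and what the lists lack is its continuation through later dosing. The other is that the trial as a whole has no repeat testing. The available text cannot show that.

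This is a cheap improvement worth making. It has no bearing on the endpoints or the planned descriptive analysis.

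**What to change.** Check the Schedule of Events and consent form first. If they already require repeat tests, align the visit lists in section V.a with them.

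If they do not, add the existing urine pregnancy test for females of childbearing age to the pre-treatment lists of treatments 2, 3 and 4, and of treatment 1 when screening was on an earlier day. State that no injection is given after a positive test. The interval from test to injection then becomes 0 days at each of these sessions.

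No new rule for follow-up or analysis is needed, since a subject who stops continues to the Week 4 and Week 12 visits as already written.

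The cost is a short amendment, at most 15 × 3 = 45 urine kits (15 × 4 = 60 if treatment 1 is included), and a few minutes at visits already held in person.
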